- Patients unable or unwilling to provide informed consent
- Patients who are illiterate.
- Patients who are non-English speaking or reading
- Patients who are unable or unwilling to be contacted by phone after surgery on post-operative day seven
- Patients with chronic pain syndrome (evidence by daily intake of opioids for chronic low back pain, chronic headaches, or fibromyalgia).

No vulnerable populations will be approached for enrollment in this study.

Registration procedures:

Eligible subjects will be recruited by the process outlined below. Study team members will be emailed a list each week of the upcoming scheduled surgeries. The scheduled patients' electronic medical records will be reviewed and if the patient meets inclusion criteria, the patient will be approached by a study team member in the pre-anesthesia care unit on day of surgery for recruitment. Written informed consent will be documented by the use of a written consent form (attached). Each potential participant will have the opportunity to review the consent form with a physician co-investigator to discuss potential benefits and risks of participation. When all questions have been addressed, written consent will be officially obtained. All subjects will receive a copy of the signed consent form.

Protocol

Research-related procedures as part of this protocol:

[x] Device utilization/implementation – Not Investigational

Device utilization: Abdominal Binder – Category B device

Procedure Description and Details:

Screening/Eligibility Visit:

The determination for surgical procedure will be made by the patient's physician. The procedure will be scheduled by the patient's physician and then a list of all upcoming surgeries is sent to all members of the OBGYN department, including the study investigators. The list will be used to screen for patient who are eligible to participate in the study. The scheduled patients' electronic medical records will be reviewed and if the patient meets inclusion criteria, she will be approached for recruitment on day of surgery in the pre-anesthesia care unit. If patients agree to participate they will sign an IRB-approved informed consent at that time.

Randomization:

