Randomization will be performed after the patient has agreed to participate, discussed the study, and signed the informed consent form. Using a random number generator, patients will be randomized in a 1:1 ratio into either the control (no abdominal binder) or the treatment (abdominal binder) group. Envelopes will be used to mask allocation to either the treatment group (abdominal binder) or the control group (no abdominal binder). Envelopes will be opened and allocation revealed after the conclusion of the procedure.

Risks:

There is a potential risk of breech of confidential information.

There is a risk of increased abdominal discomfort and skin irritation with abdominal binder use.

Benefits:

The potential benefit to subjects enrolled in the study includes improved pain control and quicker return to pre-surgery functioning. There is no financial benefit to participation. Although the patient may benefit from improved postoperative pain control and earlier ambulation, there may not be a direct benefit to study participation.

Day of Surgical Procedure

The surgical procedure will be performed using the standard procedures established in MacDonald Women's Hospital by an attending physician with a fellow and a resident. No deviation or alteration of the surgical procedure is needed to complete this study. Patients enrolled in the study to the experimental arm will have an abdominal binder ordered with their standard post-operative orders those enrolled in the control arm will not have a binder ordered.

Postoperatively, the patient will be encouraged to wear the abdominal binder continuously throughout their hospital stay, however if they wish to remove the binder for a period of time they will be able to do so. Patients will have standard narcotic and non-narcotic pain medications ordered for use after surgery. Patients will be given a Visual Analog Scale (VAS) to rate their pain at four time points during the study; pre-operatively, immediately (at 1 hour) post-operatively in the recovery area, twelve hours post-operation, and on the morning of post-operative day one. Additionally, the post-operative day number and exact time of the patient's first ambulation will be recorded.

After discharge home:

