On discharge, patients randomized to the abdominal binder arm will be instructed to wear the binder while awake each day during the first seven days after surgery. Once the patient is more than seven days post-surgery, she may continue to wear the binder as much as she would like.

It will be discussed at the time of discharge that patients should expect a follow up phone call from a study investigator on post-operative day 7. All patients enrolled in the study will be contacted by phone by a study investigator on postoperative day seven regarding post-operative narcotic use (i.e. the number of remaining narcotic pills they have) and to give an estimate (percentage) of the amount of time the abdominal binder was worn during the first seven days. Study investigators will later review the patients' EMR to determine the quantity of narcotics they were discharged home with and calculate the total usage based on what the patient communicated on POD#7.

Patients will then continue to follow with their primary surgeon as scheduled for post-surgical follow up.

Alternatives to participation:

Subject participation in this study is voluntary. Subjects can refuse to participate or withdrawal at any time without stating a reason. Non-enrollment or withdrawal from the study will not affect their access to medical care of which they would otherwise be entitled.

Withdrawal from study participation:

There are no medical contraindications to binder use aside from a large wound that is left open to heal.

Withdrawal from the study is based on patient preference. Subjects may withdrawal at any time without stating a reason. Patients who withdrawal will remain included in the study as part of the "intention-to-treat" principle. If it is discovered that they did not give an accurate medical history or did not follow instructions for the study given by the study doctor and/or study nurse, the subject may be taken off the study at any time. Information that has already been collected will continue to be retained

Adverse Event Monitoring and Reporting:

This study will utilize the Common Terminology Criteria for Adverse Events (CTCAE) v4.03 for adverse event monitoring and reporting. The CTCAE v4.03 can be accessed from the CTEP homepage (<http://ctep.cancer.gov>). All appropriate treatment areas will have access to a copy of the CTCAE v4.03.

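### The plan's one stated binder contraindication is not an exclusion and is not checked before envelopes are opened; subjects taken off study fall outside its intention-to-treat sentence; and the primary test leaves out procedure type

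*Combined protocol and SAP*

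**What the plan says.** All references are to the combined protocol and SAP.

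- **Screening/Eligibility Visit:** records are reviewed and "if the patient meets inclusion criteria, she will be approached for recruitment on day of surgery in the pre-anesthesia care unit". Consent is signed there.
- **Randomization:** "Randomization will be performed after the patient has agreed to participate, discussed the study, and signed the informed consent form". Later in the same section: "Envelopes will be opened and allocation revealed after the conclusion of the procedure". No eligibility step is described between surgery and opening.
- **Exclusion criteria:** six entries, covering age, consent, literacy, English, day-7 phone contact and chronic pain.
- **Day of Surgical Procedure:** patients in the experimental arm "will have an abdominal binder ordered with their standard post-operative orders". Wear in hospital is encouraged, and the patient may remove the binder.
- **After discharge home:** "patients randomized to the abdominal binder arm will be instructed to wear the binder while awake" for the first seven days.
- **Withdrawal from study participation:** "There are no medical contraindications to binder use aside from a large wound that is left open to heal". On analysis: "Patients who withdrawal will remain included in the study as part of the" intention-to-treat principle. Then, for a subject who gave an inaccurate history or did not do as the study staff instructed, "the subject may be taken off the study at any time". Data already collected are retained.
- **Statistical Considerations and Study Parameters:** 88 patients, 44 per arm, 80% power, alpha 0.05. The primary comparison of morphine equivalents is an unadjusted t-test or Mann-Whitney U. Type of procedure is collected, but its only stated use is descriptive (Aim 4).

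**The concern.** **Eligibility.** The contraindication appears only in the withdrawal section. As written, a patient who has it can meet every eligibility criterion, be allocated to the binder and have one ordered. No section says how she is handled or analysed. The timing wording adds an ambiguity. Randomization is placed after consent, which is before surgery, but the arm is revealed after surgery, so it is unclear whether someone found unsuitable in between counts as randomised.

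Until the envelope is opened nobody knows the arm, so leaving a patient out then cannot bias the comparison. After opening, the contraindication matters only in the binder arm, and any removal on that ground would be one-sided.

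**Subjects taken off study.** The power to take off study those who do not follow instructions can act unequally, because only one arm has wear instructions. The intention-to-treat sentence mentions those who withdraw and no one else. The outpatient part of the primary endpoint comes from the day-7 call, and nothing says that a subject taken off earlier is still called.

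**Procedure type.** Any scheduled pelvic surgery with a planned overnight stay qualifies. If opioid use differs by procedure, an unadjusted test gives up precision that a variable already on the data sheet could recover.

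**Working it through.** **1. The plan's own figure.** No mean difference or SD is given, so 88 can be neither confirmed nor called wrong. It can be inverted. With two-sided alpha (assumed; sidedness is not stated), the normal approximation gives d = (1.960 + 0.842) × √(2/44) = 0.597 SD. The noncentral t gives d = 0.604 for 80.0% power. I use 0.604.

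**2. Affected patients kept in their arm with no benefit.** Let f be the share with such a wound. The documents give no rate, so f is assumed. The diluted effect is 0.604 × (1 − f). The chance of at least one such patient in the binder arm is 1 − (1 − f)^44.

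| f (assumed) | diluted d | power | chance of ≥1 in 44 | expected, 44 × f |
|---|---|---|---|---|
| 0.5% | 0.601 | 79.6% | 19.8% | 0.22 |
| 1% | 0.598 | 79.2% | 35.7% | 0.44 |
| 2% | 0.592 | 78.4% | 58.9% | 0.88 |
| 5% | 0.574 | 75.9% | 89.5% | 2.2 |

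The loss is 0.4 to 1.6 points for f from 0.5% to 2%, and 4.1 points at 5%. The fourth column only restates the assumed f.

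**3. One-sided removal.** Suppose a share g of the binder arm is removed, and those patients' mean use differs from that of the remaining patients by k SD. The full-arm mean is then the remaining mean plus g × k, so removal shifts the comparison by g × k SD. One patient of 44 gives k/44 = 0.023k; two give 0.045k. The documents give neither g nor k, so size and direction are unknown. Without removal the shift is zero.

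**4. Adjusting for procedure.** Let R² be the share of within-arm variance explained by procedure (assumed; the documents give none). With groups balanced between arms, the effective difference is 0.604/√(1 − R²) on 85 df (two groups). The simulations used 40,000 trials per setting, 44 per arm, unstratified allocation, and groups split 30/70, 50/50 or 30/40/30. The rank simulation used log-normal use with a shift of 0.604 × √(π/3) = 0.618 SD on the log scale.

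| R² (assumed) | 0.604/√(1 − R²) | formula power | linear model, simulated | van Elteren, simulated |
|---|---|---|---|---|
| 0 | 0.604 | – | 78.7–79.4% | 78.3–79.0% |
| 0.02 | 0.610 | 80.8% | 79.9–80.3% | 78.8–80.1% |
| 0.05 | 0.620 | 82.0% | 81.1–81.6% | 80.1–81.1% |
| 0.10 | 0.637 | 84.0% | 82.8–83.8% | 82.1–82.9% |
| 0.20 | 0.675 | 87.9% | 87.0–87.7% | 86.7–87.2% |

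The unadjusted t-test and Mann-Whitney stayed at 79.6% to 80.3%, and type I error was 4.8% to 5.3% for all tests. Against 80%, adjustment loses about 1 to 2 points at R² = 0 and breaks even at about 2% to 5%. At 10% to 20% it gains about 3 to 8 points with the linear model and about 2 to 7 with van Elteren.

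**The case against.** **The wound scenario is inferred.** No section says such wounds are expected after these scheduled operations, how often they occur, or when they become known. That stands, and the rates above are illustrations only.

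**The protocol already warns of the contraindication.** It states it in its own text, the binder is not investigational, the patient may remove it, and care follows usual standards. Nothing obliges a clinician to apply a binder against that sentence. This also stands: a reader might infer that the plan forces binders on such patients, and it does not. It still gives no rule for their eligibility or analysis.

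**There is an unbiased option after opening.** The patient can stay in her allocated arm for analysis without wearing the binder. This is correct, and it is what step 2 assumes. The plan does not say that it will be done.

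**Removal from the study is not removal from the analysis.** A patient told not to wear a binder has not disobeyed, other instructions apply to both arms, and collected data are retained. This stands in part. The text permits exclusion from the analysis without requiring it; retaining data is not a commitment to analyse it.

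**Adjustment is a preference.** The planned test is valid, no figure in the documents links procedure to opioid use, and the change can cost power. This stands, so adjustment is offered as a cheap improvement.

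**Record review is not the only eligibility check.** Consent discussions and willingness to take the call also play a part. This is correct; the gap is the absence of any step after surgery.

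**Conclusion.** The point holds in three parts of different weight.

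1. The sections on exclusion, allocation, ordering and withdrawal do not fit together on the stated contraindication. This is mainly a matter of safety and consistency. The power effect is 0.4 to 1.6 points at an assumed 0.5% to 2%.
2. The route to bias through subjects taken off study is open in the wording. Its size cannot be derived from the documents.
3. Leaving out procedure type costs precision only. The gain or loss depends on an R² that the documents do not give.

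A reader might infer that opening envelopes after surgery is a flaw. It is not: it protects concealment and keeps the operating team unaware of the arm. It also means that the procedure performed cannot have been influenced by knowledge of the allocation, which makes procedure type a legitimate covariate. A reader might also infer that the primary result will be biased or that the t-test or Mann-Whitney U is invalid. The documents support neither. Withdrawn patients are kept in, and bias would need one-sided removal, which the text allows but does not prescribe.

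**What to change.** 1. Reconcile the exclusion criteria, Randomization, Day of Surgical Procedure and Withdrawal sections on the contraindication. The clinical content is for the investigators to settle.
2. Reconfirm and record eligibility under the reconciled criteria after surgery and before the envelope is opened. Patients who fail are not randomised, are reported in the patient flow and do not count toward 88. This may require stating that randomisation occurs when the next sequentially numbered sealed envelope is opened.
3. State that every patient whose envelope has been opened is analysed in her allocated arm, whether or not the binder is worn and including anyone taken off study. She still receives the day-7 call unless she declines.
4. As a cheap improvement, define two or three procedure groups before any data are compared by arm and include them in the primary analysis. Use a linear model with arm and group, or van Elteren's test as the rank version. Fix the choice between them without looking at results by arm, because they address different hypotheses. Two groups lose slightly less power than three if the rank test is likely. Stratified allocation is not needed.

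**Cost.** Protocol wording, one line on the case report form and a little more analysis. If 1% to 5% fail the recheck (assumed), 88/0.99 = 88.9 to 88/0.95 = 92.6, so about 89 to 93 consented patients yield 88 randomised. Any change to envelope logistics cannot be costed, because the documents do not say how envelopes are numbered or held across the listed facilities. Adjustment risks about 1 to 2 points of power if procedure proves unrelated to opioid use.

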Adverse event monitoring and reporting is a routine part of every clinical trial. If an adverse event does occur, the first event will be clearly identified and the severity of the event will be graded using the CTCAE. Next, whether the event is expected or unexpected will be determined and whether the adverse event is related to the medical treatment or procedure will be clarified. With this information, it will be determined whether the adverse event should be reported as an expedited report. All expedited AE reports must also be sent to the local Institutional Review Board (IRB) according to local IRB's policies and procedures.

When assessing whether an adverse event is related to a medical treatment or procedure, the following attribution categories are utilized:

Definite - the adverse event *is clearly related* to the agent(s).

Probable - the adverse event *is likely related* to the agent(s).

Possible - the adverse event *may be related* to the agent(s).

Unlikely - the adverse event *is doubtfully related* to the agent(s).

Unrelated - the adverse event *is clearly NOT related* to the agent(s).

Clinical Safety Assessments

The following will be used in this study:

- Adverse event monitoring
- Vital signs, Pain and Distress questionnaires

Adverse Event Monitoring

For the purposes of this study, any clinical sign or symptom reported by the participant, abnormal laboratory result determined to be clinically significant by the principal investigator. Additionally, a medical diagnosis noted by medical personnel with onset or worsening from the time the participant signs the informed consent through completion of the follow up will be considered to be an AE, regardless of relationship to study procedures and treatments. More specifically, worsening of the patients baseline symptoms or function will be considered clinically significant and, as such, a reportable AE.

In addition, adverse events related to the procedures will be monitored clinically during the procedure (i.e. allergic reaction), as well as during short term follow up.

Relationship of an AE to the study intervention will be categorized as definite if the investigator feels it is incontrovertibly related to the treatment and,

- It follows a reasonable temporal sequence from administration of the treatment and,

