- Results in persistent or significant disability/incapacity.
- Congenital anomaly/birth defect diagnosed in a child of a participant who participated in this study.
- Other medically important events that in the opinion of the investigator may jeopardize the participant or may require intervention to prevent one of the other outcomes listed in the definition above.

An AE is considered non serious if it does not meet the above criteria.

Adverse Event Recording

All AEs reported by the participant or observed by study site personnel from the time the participant signs the informed consent through completion of the follow up will be recorded in the participant's study record. Laboratory values that are deemed clinically

significant will be recorded as AEs. AEs are to be recorded regardless of relationship to study procedures and treatments. The information to be recorded will include, but not be limited to, relationship of the AE to study procedures and treatments, severity, and whether the event was serious.

Adverse Event Reporting

Any serious AE and Immediately Reportable AE will be reported to the Principal Investigator. An AE form will be completed. The Principal Investigator or designee will notify the IRB, and FDA, as necessary, within the required time frames. The reporting of any serious AE will not be delayed in order to obtain additional information. Any additional information, if collected, will be reported as a follow-up to the initial report.

Serious AEs will be reported using standard forms. Follow-up information on a previously reported AE will be processed using the Follow-up forms. Follow-up information includes additions, deletions, and corrections to the initial report. Previously signed, dated, and faxed forms will not be altered to provide follow-up SAE information of any type. Any serious AE that has onset after enrollment and that is unresolved at the time the participant completes or permanently discontinues the study will be followed until the event resolves or until the participant's clinical course has stabilized.

For deaths that occur following a participant's enrollment into the study, a Record of Death as well as a copy of the autopsy report (when/if available) will be submitted to the Principal Investigator. A copy of all documentation related to the event will be kept in the site's study files.

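### No question about the two named binder harms is scheduled after discharge, so mild skin irritation and discomfort at home are likely to be under-recorded by an unknown amount, and unevenly by arm

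*Combined protocol and SAP*

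**What the plan says.** The Risks section names two harms of the intervention: "There is a risk of increased abdominal discomfort and skin irritation with abdominal binder use". No expected frequency is given for either.

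Exposure runs in two phases. In hospital (Day of Surgical Procedure), patients are "encouraged to wear the abdominal binder continuously throughout their hospital stay", with removal allowed. At home (After discharge home), they are "instructed to wear the binder while awake each day during the first seven days after surgery".

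The same section schedules one study contact after discharge. Every patient is "contacted by phone by a study investigator on postoperative day seven regarding post-operative narcotic use (i.e. the number of remaining narcotic pills they have"), with a second item asking the patient "to give an estimate (percentage) of the amount of time the abdominal binder was worn during the first seven days". After that, "Patients will then continue to follow with their primary surgeon as scheduled for post-surgical follow up"; this is routine care and is not described as a study data-collection visit.

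There is a general safety plan. Adverse Event Monitoring counts "any clinical sign or symptom reported by the participant" as an adverse event and mentions monitoring in short-term follow-up. Clinical Safety Assessments lists questionnaires on pain and distress without time points. Adverse Event Recording covers "All AEs reported by the participant or observed by study site personnel", from consent to the end of follow-up. The last scheduled pain score is on day one. Study Parameters lists post-operative complications but neither named harm.

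**The concern.** The protocol identifies what the binder might do to patients and then plans no direct question about it for the part of the exposure that staff cannot see. At home, a mild rash or an uncomfortable binder enters the data only if the patient raises it, or if a caller happens to ask.

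Three things are at stake.

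- **Harm counts by arm.** Aim 4 is to describe associations between binder use and complications. Envelopes are opened at the end of the procedure, and a binder cannot be hidden from its wearer or from a caller who asks about wear time. That wear question invites binder patients to talk about the device and gives control patients little comparable cue. Unprompted reports from the two arms are therefore not on the same footing.
- **Interpretation of a null result.** The call asks how much the binder was worn but not why it was left off. If opioid use does not differ and wear is low, the trial cannot say whether discomfort or skin problems were the reason.
- **Any later statement on tolerability.** A low count could mean few harms or few reports, and the data could not separate the two.

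**Working it through.** **Does any scheduled item ask about the named harms after discharge?**

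| Source | Covers the period at home? | Asks about skin or binder discomfort? |
|---|---|---|
| Pain scores (Day of Surgical Procedure; Study Parameters) | No, the last is on day one | No, they rate pain |
| Day-seven call (After discharge home) | Yes | Not among the two items described |
| Surgeon follow-up (After discharge home) | Routine care | Not specified |
| Pain and distress questionnaires (Clinical Safety Assessments) | No time points given | Content not specified |
| Adverse event rules (Adverse Event Monitoring; Adverse Event Recording) | Yes, to the end of follow-up | No question set; reported or observed events |
| Post-operative complications (Study Parameters) | Not specified | Neither harm listed |

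No row supplies a scheduled question.

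**What would incomplete capture do?** The plan states no figure for harms, so there is none to reproduce. The only input from the documents is n = 44 in the binder arm (Statistical Considerations). The true rate p and the share of cases captured c are assumptions, shown over a range.

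- Expected recorded cases = 44 × p × c.
- Chance of recording none = (1 − p × c)^44.

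| True rate p | Capture c | Expected recorded | Chance of none |
|---|---|---|---|
| 5% | 100% | 2.2 | 0.105 |
| 5% | 50% | 1.1 | 0.328 |
| 5% | 25% | 0.6 | 0.575 |
| 10% | 100% | 4.4 | 0.010 |
| 10% | 50% | 2.2 | 0.105 |
| 10% | 25% | 1.1 | 0.328 |
| 20% | 100% | 8.8 | <0.001 |
| 20% | 50% | 4.4 | 0.010 |
| 20% | 25% | 2.2 | 0.105 |

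For example, at p = 10% and c = 50%: 44 × 0.10 × 0.50 = 2.2, and 0.95^44 = 0.105.

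**What would zero recorded cases exclude?** The one-sided 95% upper limit on the recorded rate is 1 − 0.05^(1/44) = 0.066. With full capture, that is also the limit on the true rate. At 50% capture the true rate could be as high as 0.066 / 0.50, about 13%.

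**How much wear falls at home?** The documents give only a stay of at least one night. Assume full adherence over seven days, 24 hours a day in hospital and 16 waking hours a day at home:

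- One night: 6 × 16 = 96 of 24 + 96 = 120 hours, 80%.
- Two nights: 5 × 16 = 80 of 48 + 80 = 128 hours, about 62%.
- Three nights: 4 × 16 = 64 of 72 + 64 = 136 hours, 47%.

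The home share is substantial in each case, but whether it is the larger part depends on length of stay.

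**The case against.** The strongest reply is that the protocol already has an adverse event plan that reaches past discharge. A symptom mentioned on day seven would be recorded, and wording about events reported by the participant does not exclude prompted reports. Pain and distress questionnaires are solicited instruments, the investigators review adverse events monthly, and post-operative complications are collected. All of this is true, and it rules out saying that the trial has no safety collection or that only volunteered events can be recorded. It does not close the gap, because none of these elements has a stated question on skin or binder discomfort at a stated time after discharge.

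A reader might go further and infer that the call will not ask about harms and that the trial will certainly under-count them. The documents do not support that certainty. They state the topics of the call; they contain no call form or case report form, and they give no capture rate. Nor do they establish that most wear happens at home. The 6.6% limit for zero of 44 is no evidence of a gap either: it assumes full capture and reflects sample size alone.

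It is also fair that tolerability is not an objective, that the device is marked as not investigational, and that the wear percentage is already collected. These points keep the matter minor. Finally, binder-caused irritation has no control-arm counterpart, so some imbalance in what patients mention is inherent in the comparison.

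**Conclusion.** The point holds as a low-severity, inexpensive improvement. The protocol names two binder harms and schedules no question about either after discharge. Mild events at home are therefore likely to be under-recorded, and unevenly by arm, since participants and callers know the allocation. The direction is an inference from how reports would arise, and the amount is unknown.

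The size can only be illustrated. With an assumed true rate of 10%, moving from full to 25% capture lowers the expected count from 4.4 to 1.1 and raises the chance of an empty harm record from 1% to 33%. Even at 50% capture, the chance of recording at least one case is about 90%, so the likelier consequence is a count that is too low and not comparable between arms, rather than none at all. The primary comparison of opioid use is not affected.

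**What to change.** Add to the day-seven call, after the pill count has been recorded so that the new items cannot influence it:

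1. In both arms, in identical words, a yes/no item on skin irritation of the abdomen since surgery.
2. In both arms, in identical words, a yes/no item on abdominal discomfort limiting activity.
3. In the binder arm only, whether the binder was left off for either reason.

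Add these to Study Parameters and report them by arm with exact confidence intervals.

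The cost is about one extra minute per call. The discomfort item will also pick up surgical pain and is answered with allocation known, so it should be read as a comparison between arms and not as a rate attributable to the binder. Prompted answers can still be coloured by knowledge of allocation; identical wording makes the prompt equal but does not remove that. The total of 88 patients and the primary endpoint stay as they are.
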